This study is powered to detect a clinically significant difference between iCBT and the usual care conditions. Meta-analysis of medical and behavioral outcomes indicates that a medium effect-size between conditions will have a significant impact on quality of life. In a previous study we observed an average effect of about $d=0.55$ SD. To allow for a somewhat smaller effect in this proposed study, we design our study to have 80% power to detect clinically significant effect of $d=0.5$ SD. In the pilot data, we found a within-subject correlation structure consistent with a stationary autoregressive process with correlation parameter 0.4. We also assume a dropout rate of 20% for these power calculations. With these assumptions on effect size, covariance structure, and dropout rates, and with a two-sided alpha level of 0.05, the methods of Hedeker et al.⁸⁶ estimate that a sample size of 48 subjects per group will provide 80% power for the test of our primary hypothesis.

We believe that this is a conservative estimate, based on the larger effect size observed in our prior study, and the higher than expected dropout rate used in the calculation. In addition, our analyses will use the baseline measure of Psychosocial Functioning as a covariate, which should reduce the standard errors in our test, and therefore increase the smallest detectable effect size.

4.2. Define plans for data and statistical analysis, including key elements of the statistical plan, stopping rules and endpoints.

Planned Analyses

(i) Overview

Logistic, log-linear and linear random effects models (hierarchical regression models) will be implemented with random intercepts and slopes for longitudinal binary, count, and continuous outcomes, respectively. These models will contain separate main effects for change from baseline to each follow-up visit at 6, 12, and 18 months, main effect for the treatment, and interactions between the visit and treatment indicator variables. For each of the primary (workforce participation indices) and the secondary (Work Behavior Inventory, Specific Levels of Function) outcomes, separate intent-to-treat (ITT) tests and estimates (with 95% confidence intervals) of randomized group contrasts at 6, 12, and 18 months will be obtained from the estimates of the respective time-treatment interactions.

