We will assess residuals in the longitudinal linear random effects model with normal QQ plots and estimation of the skewness and kurtosis coefficients. If these are coefficients exceed their classical cut-offs of 3 and the QQ plots confirm skewness and/or kurtosis, we will then perform a longitudinal analysis based on a random effects generalized linear model with a gamma error distribution (with SAS Proc GLIMMIX) that handles skewed and kurtotic distributions. We will fit such a model with identity link function (linear mean model), such that the resulting estimates and tests are comparable to those of the normal error random effects model. We will compare the estimates and p-values. If the two approaches agree with respect to significance at the specified alpha level, then we will use the results from the linear random effects model with normal error. If they disagree we will base results on the gamma error distribution model.

Prior to each hierarchical analysis, baseline outcomes, pre-treatment assessment scores, and demographics (except gender which by definition is balanced due to be a stratification factor in the randomization) will be compared between the two treatments at the two-sided alpha = .05 level. Any significant baseline variables will be included as covariates in the hierarchical regression models. We will also perform as a sensitivity analysis based on an adjustment of the ITT models for post-randomization confounding due to differences in medication patterns between the randomized groups. Such adjustments will be based on a causal modeling approach that distinguishes between direct effects of the iCBT intervention, on the one hand, and differences in medication patterns, on the other, using randomization and its products with baseline covariates as the instrumental variables to control for unmeasured confounding due to choice of medication.

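### Covariates are picked by baseline significance tests, the functioning covariate promised in the power section has no instrument and no place in the listed model, and how baseline enters is unsettled: prespecify all three

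*Combined protocol and SAP*

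**What the plan says.** Three statements bear on covariates.

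- **Screen (W.4.2, (i) Overview).** "Prior to each hierarchical analysis, baseline outcomes, pre-treatment assessment scores, and demographics" are compared between arms at two-sided 0.05. Then: "Any significant baseline variables will be included as covariates in the hierarchical regression models". This is the only covariate rule in the analysis section. Gender is exempt: "except gender which by definition is balanced due to be a stratification factor in the randomization".
- **Promise (W.4.1, Power analysis).** After deriving 48 per group, the section adds that "our analyses will use the baseline measure of Psychosocial Functioning as a covariate, which should reduce the standard errors in our test". It names the construct but no instrument. Table 1 in O.1.3 lists WHODAS, SLOF and UPSA at baseline, and any of them could be meant.
- **Model (W.4.2, (i) Overview).** "Logistic, log-linear and linear random effects models (hierarchical regression models) will be implemented with random intercepts and slopes". "These models will contain separate main effects for change from baseline to each follow-up visit at 6, 12, and 18 months", together with a "main effect for the treatment, and interactions between the visit and treatment indicator variables". The "randomized group contrasts at 6, 12, and 18 months will be obtained from the estimates of the respective time-treatment interactions". Neither a functioning covariate nor gender is among the listed terms.

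**The concern.** When arms are randomised, a significant baseline difference is a chance event. Testing for it says nothing about whether the variable predicts the outcome, so the screen leaves strong predictors out about 95% of the time and lets in unrelated ones about 5% of the time. W.4.1 offers a precision gain from a functioning covariate as one reason to call its estimate conservative, yet nothing in W.4.2 delivers that gain.

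Whether any covariate can help depends on how baseline enters, and the text allows several readings. Three visit-by-treatment interactions beside a treatment main effect need a fourth, reference visit. That points to baseline as a response whose arm difference is left free. The words about change from baseline could also mean change scores as responses. Follow-up values alone as responses is a third possibility. With 96 participants and an 80% power target, precision is what is at stake.

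**Working it through.** **1. The plan's own figure.** Inputs from W.4.1: d = 0.5 SD, two-sided alpha 0.05, 80% power, AR(1) correlation 0.4, 20% dropout. Assumptions: unit SD, a contrast averaging 6 and 12 months (the window used in W.4.2 (ii) and (iii)), and dropout rising evenly to 20% at 18 months.
- Variance of the two-visit average = (1 + 0.4)/2 = 0.70.
- Complete-data n = 2 × 0.70 × (1.960 + 0.842)² / 0.5² = 44 per group.
- With the assumed dropout, 49 per group are needed and 48 give 79.9% power, with no covariate.

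A second set (own baseline adjusted, 20% lost by month 6) gives 79.4% at 48. The documents do not say which was used. Neither needs a separate functioning score, and W.4.1 presents that covariate as an extra.

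**2. How often chance changes the model.** Table 1 has 18 baseline rows; leaving out SCID, Risk Assessment and Check-in leaves 15. Expected entries = 15 × 0.05 = 0.75. P(at least one) = 1 − 0.95¹⁵ = 54% if independent, and 41% at an assumed inter-correlation of 0.4. This describes the screen; it is not an error rate.

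**3. Cost of screening where covariates act.** Let r be the correlation of the covariate with the response. Relative variances are 1 unadjusted and 1 − r² always adjusted. The screen keeps the share E[z²; |z| > 1.96] = 2(1.96 × 0.0584 + 0.025) = 0.279 of the gain r².
- r = 0.2: (1 − 0.279 × 0.04)/0.96 = 1.030; simulated 1.022.
- r = 0.4: (1 − 0.279 × 0.16)/0.84 = 1.137; simulated 1.129.

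The simulations (200,000 trials per r, 48 per arm) include the small cost of estimating the coefficient, so they are the figures to use: about 2% and 13%. For follow-up values adjusted for own baseline, AR(1) 0.4 implies r = 0.4, 0.4² = 0.16 and 0.4³ = 0.064. The simulated ratios are 1.129, 1.011 and 0.995, so about 13% at 6 months, 1% at 12 and nil at 18. These AR(1) figures do not carry over to change scores, whose correlation with baseline depends on SDs that the documents do not give.

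If 80% power holds without the covariate, always adjusting gives Φ(2.80/√(1 − r²) − 1.96), about 82% at r = 0.2 and 86% at r = 0.4.

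**4. Type I error.** With an assumed 42 evaluable per arm and 20,000 null runs, test-then-adjust rejected 4.6% at r = 0.2, 4.4% at r = 0.5 and 3.7% at r = 0.7. There is no inflation.

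**5. Baseline as a response with a free arm difference.** Each interaction estimates the arm difference in (value at visit t − value at baseline). A covariate main effect adds the same amount to both values and drops out. A generalised least squares check with four visits, under AR(1) 0.4 and under a random intercept-and-slope covariance, found the contrasts with and without the covariate equal to within 1e-14 in complete data. With 20% random dropout, the variance changed by about 0–2%. This applies to the linear model only; it was not shown for the logistic, log-linear or gamma models.

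**6. Difference in change against own-baseline adjustment.** Variance ratio = (1 + k² − 2rk)/(1 − r²), with k = baseline SD / follow-up SD.

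| k | 6 months (r = 0.4) | 12 months (r = 0.16) | 18 months (r = 0.064) |
|---|---|---|---|
| 1 | 1.20/0.84 = 1.43 | 1.68/0.9744 = 1.72 | 1.872/0.9959 = 1.88 |
| 0.5 | 0.85/0.84 = 1.01 | 1.09/0.9744 = 1.12 | 1.186/0.9959 = 1.19 |
| 0.25 | 0.8625/0.84 = 1.03 | 0.9825/0.9744 = 1.01 | 1.0305/0.9959 = 1.03 |

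A small k is plausible for work outcomes: O.2.1.1 scores the WBI as 0 for anyone not working, so baseline may vary little.

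**The case against.** The best defence is that little is lost. The screen forfeits 72% of the gain, but the gain is only r², so the extra variance is 2% at r = 0.2 and, at the plan's own correlation, is notable only at 6 months. On the reading that the interaction wording favours, the screen does not alter the linear contrasts in complete data at all. All of this stands, and it limits the size of the point. It does not defend the rule, since no reading makes it the better method and nothing elsewhere in the documents repairs it.

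Four stronger inferences are tempting, and the documents do not support them.

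- *The screen produces false positives.* It does not; the test is slightly conservative.
- *W.4.1 and W.4.2 contradict each other.* The screened variables may be meant to add to the promised covariate. The construct is named, and what is missing is the instrument and the model term. This is an omission to reconcile.
- *The trial is underpowered because the contrasts are differences in change.* With equal SDs, the 6–12 month average has variance 0.70 + 1 − 2 × 0.28 = 1.14, where 0.28 = (0.4 + 0.16)/2. Complete-data power at 48 per arm is then about 63%. With a baseline SD half as large, the variance is 0.70 + 0.25 − 0.28 = 0.67 and power is about 85%. The documents give no baseline SDs and do not settle this reading.
- *Leaving gender out is a serious fault.* Stratification keeps it near balance, adjustment is not prohibited, and the omission probably costs little.

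**Conclusion.** The point holds as a matter of precision and specification. Covariates are selected by chance, the promised functioning covariate is not carried into the model, and the role of baseline is open, so the gain offered in W.4.1 is not secured.

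The size depends on the reading, and the following are alternatives that must not be added together.
- **Follow-up values or change scores as responses:** about 2% to 13% extra variance for assumed correlations of 0.2 to 0.4.
- **Baseline as a response with a free arm difference:** no covariate gain in the linear model with complete data. The penalty against own-baseline adjustment runs from 43–88% with equal SDs down to about 1–3% if the baseline SD is a quarter of the follow-up SD.

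These sizes rest on assumed correlations and SD ratios, and on the pilot AR(1) value applying to these outcomes. The change should be made because it is nearly free; the case for it does not depend on the validity of the test or on the sample size.

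**What to change.** 1. Delete the significance screen from W.4.2 and report baseline tables descriptively.
2. Prespecify one covariate set for the primary and secondary models: gender (the stratification factor), the outcome's own baseline value, and one named functioning score that is already collected. The choice of score is the sponsor's. SLOF total is one option; for the SLOF outcome its own baseline serves as this score and is not entered twice.
3. State one baseline method. The simplest is baseline as a covariate with 6, 12 and 18 months as the responses. A longitudinal model with a common baseline mean and covariate-by-visit terms is an alternative. Do not combine them.
4. Before unblinding, and on pooled data, decide whether gender or own baseline must be left out of any logistic or log-linear model because of sparseness. The documents give no expected share of women; an assumed 5–20% of 96 is about 5 to 19.
5. Align W.4.1 with W.4.2. Also correct the direction in W.4.1: smaller standard errors reduce the smallest detectable effect.

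Cost: a few sentences and no new data. The simple version uses about 2 to 3 degrees of freedom. The common-baseline version uses up to about 8 coefficients (two covariates × four visits).

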- K. **Primary Outcome Variable(s)** (Define the primary outcome variable(s) used to support the study objectives (e.g. if the objective is to show that treatment A is superior to treatment B in the treatment of subjects with essential hypertension, the primary outcome variable is blood pressure measurement.): **Our primary specific aim is to determine whether iCBT will significantly improve work outcomes at post-treatment to a greater extent than usual care in low functioning patients with schizophrenia who are enrolled in SE. The primary outcome measures are several work-related indices of work participation across the 18 months of active study involvement, including the following: 1) instances of job attainment, 2) average days worked per week while employed, 3) average number of hours worked per week while employed, 3) total weeks worked , and 4) a composite of these indices.**
- L. **Secondary Outcome Variable(s)** (Define the secondary outcome variables. Such measured variables should also include the timing of measurement.): **The second trial outcome measures will include the Work behavior Inventory (WBI) and the Specific Levels of Functioning Scale (SLOF). A significant ITT difference on the WBI and the total SLOF score across 6 and 12 months would support the hypothesis that ICBT is more efficacious than usual care at improving functioning by the end of treatment (Secondary Aim 1). Similarly, WBI score and the SLOF total score at 18 months is a secondary outcome, and the separate ITT effects on functioning at 18 months with the respective month-treatment interaction in favor of iCBT would support the hypothesis that it promotes better functioning than usual care during the 6 months after the completion of treatment (Secondary Aim 3).**
- M. **Study Design and Methods:**
 1. Is this a clinical trial? YES NO (Randomized non-drug/non-medical device intervention)
 - 1.1. If yes, what type? Check all that apply.
 Phase I Phase II Phase III Phase IV
 - 1.2. If yes, this study must be registered on [Clinicaltrials.gov](https://clinicaltrials.gov).

2. Design

2.1. What research methods will be used in the project? Check all that apply.

 Surveys/Questionnaires	 Interviews	 Audio Taping
 Behavioral Observations	 Chart Reviews	 Video Taping

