Beck Cognitive Insight Scale (BCIS).⁶⁷ The BCIS is a 15-item measure of two components (factors) of cognitive insight—the capacity and willingness to observe one’s experiences and consider alternative explanations (self-reflectiveness) and the overconfidence in the validity of one’s beliefs (self-certainty). Sample items include, “There is often more than one possible explanation for why people act the way they do” and “My interpretations of my experiences are definitely right.” In the original study with inpatients of varying diagnoses, the BCIS showed adequate convergent and discriminant validity and internal consistency ($\alpha = .60-.68$). The original psychometrics and factor structure have now been replicated several times.⁶⁹ Taken together, the research on the BCIS suggest that cognitive insight has important clinical significance for people with schizophrenia, that it may be a mediating variable in cognitive therapy for the disorder, and that it should therefore be assessed and addressed in clinical trials.⁶⁹

Collection of information from the Work Behavior Inventory (WBI).⁵⁵ The WBI is a 35-item scale specifically designed to assess the work behaviors of individuals suffering from severe mental illness. The WBI is completed as a routine standard of care measure during Supported Employment procedures. As part of usual care, the SE Specialists observes the patient in his/her work setting and also speak to the subject’s supervisor (when the veteran allows this). As part of the research study, we will collect information from the WBI at the time of the baseline and follow-up assessments. The measure will have a value of ‘0’ at points in which the participants are not working. WBI data may be missing if research participants refuse to allow the SE specialist to observe at the worksite and/or speak to employers. Data from the WBI will be analyzed along with other research data whenever available. The WBI is broken down into specific areas, including social skills, cooperativeness, work habits, work quality, and personal presentation. Each item is scored on a 5-point scale, with higher totals indicating stronger work performance. The WBI has been found to have good validity and reliability⁵⁵ and predicts vocational outcomes and productive activity after discharge from rehabilitation.

Performance measures

a) Cognitive

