While the present study is designed to minimize lost observations, the proposed random effects or hierarchical regression approach is superior to last observation carried forward in minimizing bias and Type 1 error and inferentially equivalent to multiple imputation.⁷⁹ To assess the sensitivity of treatment effect estimates to missing data, we will compare the results under the above hierarchical regression models with those based on shared parameter models that account for informative missingness that is dependent on unobserved outcomes through a latent variable.⁸⁰ If the results between the two approaches are similar then we will present the proposed hierarchical regression models as robust to informative missing data; otherwise we will note that the results may be

sensitive to informative missing data and augment them with those based on the shared parameter model.

(ii) **Work outcome.** The primary trial outcome measure, workforce participation (composite index) at 6, 12 and 18 months analyzed in the manner described above. A significant ITT difference on the total WBI score across 6 and 12 months would support the hypothesis that iCBT is more efficacious than usual care at improving work outcomes by the end of treatment (Primary Aim 1). Similarly, WBI score at 18 months is a secondary outcome, and a separate ITT effect on work outcomes at 18 months with the respective month-treatment interaction in favor of iCBT would support the hypothesis that it promotes better work outcomes than usual care during the 6 months after the completion of treatment (Secondary Aim 2).

(iii) **Functional outcome.** The second trial outcome measures include the Work Behavior Inventory and the total score on the Specific Levels of Functioning Inventory (SLOF) at 12 months A significant ITT difference on the WBI and the total SLOF score across 6, 12 months would support the hypothesis that ICBT is more efficacious than usual care at improving functioning by the end of treatment (Secondary Aim 1). Similarly, WBI and SLOF total score at 18 months is a secondary outcome, and the separate ITT effects on functioning at 18 months with the respective month-treatment interaction in favor of iCBT would support the hypothesis that it promotes better functioning than usual care during the 6 months after the completion of treatment (Secondary Aim 3).

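### The only criterion stated for Primary Aim 1 uses the WBI, a secondary outcome; the composite named as primary has no formula and no score for participants without a job

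*Combined protocol and SAP*

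**What the plan says.** All references are to the combined protocol and SAP.

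- **W.4.2 (ii), first sentence**, names the primary: "The primary trial outcome measure, workforce participation (composite index) at 6, 12 and 18 months analyzed in the manner described above".
- **W.4.2 (ii), second sentence**, gives the supporting result: "A significant ITT difference on the total WBI score across 6 and 12 months would support the hypothesis" that iCBT is better at "improving work outcomes by the end of treatment (Primary Aim 1"). The label Primary Aim 1 appears nowhere else. Section K states the primary aim without a decision rule.
- **W.4.2 (iii)** uses the same WBI comparison, with the SLOF, for Secondary Aim 1: "A significant ITT difference on the WBI and the total SLOF score across 6, 12 months would support the hypothesis".
- **Sections K and O.1.1** list the primary as job attainment, "average days worked per week while employed, 3) average number of hours worked per week while employed", total weeks worked, and a composite of these. No section gives a formula, weights or scaling for the composite.
- **Section O.2.1** assigns the WBI a value of zero "at points in which the participants are not working", and adds that "WBI data may be missing if research participants refuse to allow the SE specialist to observe at the worksite and/or speak to employers". No such rule is given for the workforce indices.
- **W.4.1** calls the composite the primary outcome and the WBI secondary, and states 80% power with 48 per group.

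**The concern.** The sentence that attaches a result to Primary Aim 1 names the wrong variable. Taken at face value, a positive WBI result would allow the primary aim to be reported as supported whatever the composite showed. One WBI comparison would also serve both a primary and a secondary aim.

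Correcting that word does not finish the job, because the composite cannot be computed from the plan. With no formula, it could be built after the data are seen. If participants without a job are left unscored on the two averages taken over employed time, those components compare only people who found work after randomization. That is not the intent-to-treat comparison promised in W.4.2 (i).

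**Working it through.** **1. Are the WBI and the composite the same thing?** No.

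- Sections L, O.1.1, O.2.2, W.4.1, W.4.2 (i) and W.4.2 (iii) all place the WBI among the secondary outcomes.
- W.4.2 (vi) lists the composite, the WBI total and the SLOF total as three separate dependent variables.
- Section O.2.1 describes the WBI as a 35-item rating of work behaviour. The workforce form records jobs, days, hours and weeks. A working participant can lack a WBI by refusing worksite observation and still have workforce data.

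**2. Is the primary otherwise settled?** Not fully.

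- *Content.* W.4.1 and W.4.2 (ii) have one composite. K and O.1.1 have four indices plus the composite. W.4.2 (i) speaks of indices in the plural. O.2.2 adds total income and omits the composite.
- *Time frame.* K refers both to post-treatment and to the full 18 months. W.4.2 (ii) uses 6 and 12 months for Primary Aim 1 but does not define this as one contrast. W.4.2 (i) plans separate tests at 6, 12 and 18 months.
- *No job.* Job attainment and weeks worked have a natural zero, though the plan does not say so. The two averages over employed time are undefined.
- *Window.* The workforce form is completed every 3 months (Table 1). The plan does not say whether total weeks worked is cumulative or per interval.
- *18 months.* W.4.2 (ii) opens Secondary Aim 2 with the WBI, then refers to "a separate ITT effect on work outcomes at 18 months with the respective month-treatment interaction in favor of iCBT". W.4.2 (iii) uses the WBI at 18 months again, for Secondary Aim 3. The composite at 18 months has no clear aim.

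**3. Can the stated 80% be reproduced?** Inputs from W.4.1: d = 0.5, two-sided alpha 0.05, AR(1) correlation 0.4, 20% dropout, 48 per group. The contrast and dropout timing are not given, so I tried several. Normal approximation, unit variance, equal effect at each visit, power = Φ(d/SE − 1.96).

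For the average of the 6- and 12-month differences, without baseline covariate, the variance factor is (1 + 0.4)/2 = 0.70.

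| Dropout timing | SE | d/SE | Power |
|---|---|---|---|
| Even build-up to 20% at month 18 (93.3%, 86.7%, 80% observed) | 0.1788 | 2.796 | 79.9% |
| 10% lost by month 6, 20% by month 12 | 0.1834 | 2.727 | 77.8% |
| 20% missing at both visits: √(2 × 0.70/38.4) | 0.1909 | 2.619 | 74.5% |

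A baseline-adjusted 6/12-month mean also comes close: variance 0.6216, n = 2(1.96 + 0.8416)² × 0.6216/0.25 = 39.0, and 39.0/0.8 = 48.8 per group.

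A separate 12-month test, the kind that W.4.2 (i) does plan, has lower power. With 20% missing, SE = √(2/38.4) = 0.2282 and power is 59%. With even build-up, SE = 0.2180 and power is 63%.

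**4. Illustrations on assumed values.** None of the WBI effects, correlations or employment rates below is in the documents.

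- *WBI criterion alone*, SE 0.1788: a significant result favouring iCBT occurs in 2.5%, 29% or 80% of trials if the WBI effect is 0, 0.25 or 0.5 SD.
- *Different verdicts*, d = 0.5 on both outcomes: the two tests disagree in 27%, 23%, 17.5% or 10% of trials if the two contrasts correlate 0.3, 0.5, 0.7 or 0.9.
- *Scored only if employed*: at 30%, 50% or 70% ever working, 48 × 0.3 = 14.4, 48 × 0.5 = 24 or 48 × 0.7 = 33.6 per group have a value. After 20% dropout (38.4 per group) these become 11.5, 19.2 and 26.9.

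**The case against.** The strongest reply is that this is a wording slip. The composite is called primary in W.4.1 and in the sentence just before the WBI criterion, and W.4.2 (i) plans intent-to-treat tests of the workforce indices. A WBI difference is said only to support the hypothesis. This much stands: a reader might infer that the WBI alone decides Primary Aim 1 and that a real composite effect would be ignored, but the text states no such exclusive rule. What is missing is the sentence linking the planned composite test to the aim.

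Three other stronger readings also go beyond the documents:

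- *That the sample size is wrong.* The 80% is recovered under plausible contrasts. Equally, the match does not confirm it: the plan does not name the contrast, nor say which outcome gave the earlier effect of about 0.55 or the 0.4 correlation.
- *That type I error is inflated.* One 6/12-month contrast has 5%. Only if 6 and 12 months were each tested at 0.05, with either counting as success, would it reach about 9.3% (test correlation 0.4). The plan does not say that either visit would suffice.
- *That verdicts would disagree in a known share of trials.* Those rates rest wholly on assumed correlations. Because the WBI is zero when not working, it partly encodes employment, which makes the lowest correlation hard to defend.

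**Conclusion.** The concern holds, and the text must be corrected before analysis. The conflict is in current wording, and no other section repairs it: the composite is the declared primary, but the only stated criterion for Primary Aim 1 is on the WBI. The missing formula and missing no-job score are confirmed by reading every section that describes these measures.

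The consequence is that the aim could be declared supported on a secondary measure, or on a composite defined late. It is not that the composite goes untested or that 48 per group is inadequate. The only numerical finding that rests on the plan's own inputs is that power depends on the unnamed contrast and dropout timing: 74.5% to 79.9% for the 6/12-month average and 59% to 63% for month 12 alone. Both ranges assume no baseline covariate and that d = 0.5 and AR(1) 0.4 apply to the composite.

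**What to change.** 1. In W.4.2 (ii), replace the WBI total with the workforce participation composite in the Primary Aim 1 sentence. Keep the WBI and SLOF as secondary.
2. Name one primary contrast and its time frame, for example the average of the 6- and 12-month treatment differences at two-sided 0.05. Reconcile it with the two time frames in section K, and label the separate visit tests as secondary.
3. Before analysis, fix the composite's formula so that every randomized participant can be scored, for example zero on the two averages over employed time when there is no job, matching the WBI rule. State the reporting window for total weeks worked.
4. State that the composite, not each index, is the single primary. If the sponsor prefers to keep the indices as primary, a multiplicity rule is needed instead. Align O.2.2 with K and O.1.1, and say which outcome at 18 months tests Secondary Aim 2.
5. In W.4.1, name the contrast and dropout pattern behind the 80%.

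The cost is wording in a few sections and one formula. It needs no new data, and nothing here calls for a different sample size. The downside is that individual indices and separate visits could no longer be claimed as primary.
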